7.3.4 Safety analyses

The safety set, described in [Section 7.3](#), will be used to perform all safety analysis. In general, safety analyses will be descriptive in nature and will be based on BI standards. No hypothesis testing is planned.

Statistical analysis and reporting of adverse events will concentrate on treatment-emergent adverse events. To this end, all adverse events occurring between start of treatment and end of the residual effect period will be considered ‘treatment-emergent’. The REP is defined as 20 weeks after the last dose of trial medication. Adverse events that start before first drug intake and deteriorate under treatment will also be considered as ‘treatment-emergent’. Drug related AEs will be tabulated by system organ class and preferred term after coding according to the current version of the Medical Dictionary for Drug Regulatory Activities (MedDRA).

In addition, the frequency, severity, and causal relationship of adverse events will be tabulated by system organ class and preferred term after coding according to the current version of MedDRA.

Laboratory data will be analysed both quantitatively as well as qualitatively. The latter will be done via comparison of laboratory data to their reference ranges. Values outside the reference range as well as values defined as clinically relevant will be highlighted in the listings. Treatment groups will be compared descriptively with regard to distribution parameters as well as with regard to frequency and percentage of patients with abnormal values or clinically relevant abnormal values.

Vital signs, physical examinations, or other safety-relevant data observed at screening, baseline, during the course of the trial and at the end-of-trial evaluation will be assessed with regard to possible changes compared to findings before start of treatment.

7.4 INTERIM ANALYSES

In order to ensure the patient's safety during the trial, a partially external DMC, independent of the trial and project teams, will be set-up to review all available un-blinded safety data as well as selected efficacy data at regular intervals following first-patient-in. A DMC SAP which describes the analyses required for assessment by the DMC will be produced and finalized prior to first patient randomized into the trial. Further details will be provided in a DMC charter.

An interim analysis, on the primary endpoint only, will be performed if the period for randomization of the entire patient population exceeds approximately 4 months. The purpose will be to facilitate further substance development and project planning. There will be no changes to the design of the trial as a result of the performance of this optional interim analysis. If performed, the interim database lock and subsequent analysis will be done once the first 50% of the total required number of patients has completed 16 weeks of study. The efficacy decision that will be communicated to the sponsor will be formulated with regard to the conditional probability for achieving at least a target difference in the treatment effect at week 16 based upon the primary endpoint and the decision boundary as described in DMC

charter. Further details on the communication strategy will be provided in the DMC charter. The interim analysis will be performed by the DMC, independent of the trial team, in order to prevent the potential introduction of operational bias. Details regarding the analyses required for this interim, if required, will be described in the DMC SAP. An interim logistics plan, outlining the procedures to be implemented to ensure that all members of the trial team, including the investigators and patients, remain blinded to study treatments, will also be prepared and approved prior to achieving interim database lock in accordance with the sponsor's SOP. This logistics plan will include a list of the sponsor representatives who will have access to the un-blinded interim data via knowledge of the interim results for subsequent project planning.

An additional interim analysis will be performed once the first 75% of patients have completed 16 weeks of the study for the purpose of planning the subsequent trial(s) in PPP. This analysis will include primary, secondary, and selected further efficacy endpoints and biomarkers as well as the PK concentration data, and details of the statistical analysis will be specified in the trial statistical analysis plan. In order to protect the integrity of the continuing trial, this 75% interim analysis will be performed by a team who are external and fully independent from the trial team. The information resulting from this analysis will not be shared with patients, investigators, or with sponsor-involved trial team members. An interim analysis logistics and access plan will be prepared which will outline the team who will perform the analysis, the procedures to protect the blind, the unblinding process, and the individuals who will have access to the results and to any individual unblinded data. There are no changes to the design of the trial planned as a result of the performance of this additional interim analysis.

Once all randomised patients have completed the first 16 weeks of study, a partial database lock may be performed in order that a fast track analysis of primary and selected secondary and safety endpoints be done; a second data lock would then be done for the remaining efficacy and safety data collected up to week 16. If fast-track analysis is not performed, a single database lock will be done for safety and efficacy data collected up to week 16. At this time, the final analysis of these data through week 16 will be performed. Since the study is planned to continue through an additional 16 weeks of further follow-up, and will remain blinded, a week 16 logistics plan will be developed in order to protect the integrity of the ongoing trial data and reporting subsequent to treatment un-blind for both the fast track and the complete week 16 primary analysis. Details of the analysis to be performed for the week 16 data will be described in the TSAP which is planned to be finalized prior to achieving database lock for the optional week 16 interim analysis.

An analysis of the entire trial data will be performed once all randomized patients have completed the 32 weeks of study. At this time, the database will be locked, and official unblinding of the trial will be performed. Details of the analysis to be performed for the completed trial through 32 weeks (End of Trial Visit) will also be described in the TSAP which is planned to be finalized prior to achieving database lock for the optional week 16 interim analysis.

All analyses are planned to be documented in a clinical trial report which is to be prepared at the end of the trial.

7.5 HANDLING OF MISSING DATA

Every effort will be made to collect complete data at all visits. However, missing data will still occur and approaches to handle this are proposed below.

With respect to safety evaluations, it is not planned to impute missing values.

For all binary endpoints (i.e. endpoints that are either 1 (patient responded) or 0 (patient did not respond)), the following will be performed:

- If there are data at visits both before and after the visit with a missing outcome, then impute as success only if both neighbouring visits also represent a success;
- Otherwise, impute as a failure to achieve a response (i.e. NRI [No Response Imputation]).

If a patient takes a rescue medication for the treatment of palmoplantar pustulosis prior to observing the primary endpoint for this trial, then all data subsequent to the intake of such rescue will be considered to represent a failure to achieve a response. Further details on what constitutes a rescue intake with potential impact on efficacy outcomes will be described in the TSAP.

For secondary efficacy endpoints which are continuous in nature, the use of a restricted maximum likelihood (REML)-based mixed model repeated measures (MMRM) approach will ensure that missing data are handled implicitly, via a missing at random assumption, by the statistical model.

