3.0 DESCRIPTION OF DESIGN AND TRIAL POPULATION

3.1 OVERALL TRIAL DESIGN AND PLAN

This is a randomised, double-blind, placebo-controlled, parallel-design study. This design is appropriate for providing proof-of-concept and assessing the efficacy and safety of BI 655130 compared to placebo in patients with PPP.

There will be two active dosing arms in this study along with a placebo control arm as follows:

Figure 3.1: 1

The final analysis of the efficacy and safety data collected up to week 16 will be performed once all randomised patients have completed the first 16 weeks of study; at that time-point, a database lock will be done. The final analysis of the entire trial data collected through week 32 will be performed once all patients have completed the last scheduled trial visit.

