4.2.2 Restrictions

4.2.2.1 Restrictions regarding concomitant treatment

The medications (or classes of medications) listed in [Table 4.2.2.1:1](#) must not be taken for the time periods as specified.

Table 4.2.2.1:1 Restricted Medications

Medication or class of medications	Restriction duration (through Primary Endpoint Visit at Week 16) ¹
IL36R inhibitors other than the study drug	not allowed neither before nor during trial participation
Secukinumab (Cosentyx®), ustekinumab (Stelara®), guselkumab, ixekizumab, tildrakizumab, brodalumab Adalimumab, infliximab Natalizumab or agents that deplete B or T cells (e.g. rituximab, alemtuzumab or visilizumab) Investigational products for psoriasis	12 weeks or 5 half-lives, whichever is greater, prior to randomisation

Table 4.2.2.1:1 Restricted Medications (cont'd)

Medication or class of medications	Restriction duration (through Primary Endpoint Visit at Week 16) ¹
Etanercept Live virus vaccinations ⁴	6 weeks prior to randomisation
Other systemic immunomodulating treatments (e.g. corticosteroids ² , methotrexate, fumaric acid esters, acitretin, ciclosporin, apremilast Any investigational device or product (excludes psoriasis products)	4 weeks prior to randomisation
Phototherapy (e.g., UVA, UVB), topical treatment for psoriasis or any other skin condition (e.g. corticosteroids ³ , vitamin D analogues, salicylic acid, tar, anthralin)	14 days prior to randomisation.
Anakinra	7 days prior to randomization

¹ In case of worsening of the PPP and/or psoriasis, the use of a rescue medication is left at the discretion of the investigator (refer to Section (4.2.1.1)); In case of any other acute indication after the Primary Endpoint Visit at Week 16, the use of a restricted medication is permitted.

² There is no restriction on corticosteroids with only a topical effect (e.g. inhaled corticosteroids to treat asthma or corticosteroids drops administered in the eye or ear).

³ Exception: topical steroids of US class 6 (mild, such as desonide) or US class 7 (least potent, such as hydrocortisone) for use on the face, axilla, and/or genitalia with a restriction of use within 24 hours prior to trial visit in which ppPASI is assessed.

⁴ Live virus vaccination should be restricted until the end of the trial.

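### Does the both-neighbours rule give a missing Week 16 response different values at different data cuts?

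*Protocol*

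**What the plan says.** Protocol Section 7.5 sets one rule for all binary endpoints. If there are data before and after the missing visit, the instruction is to "impute as success only if both neighbouring visits also represent a success". The second branch reads "Otherwise, impute as a failure to achieve a response". In the Flow Chart, Week 16 (Visit 11) lies between Week 12 (Visit 10) and Week 24 (Visit 12), so a missing Week 16 response can become a success only with the help of Week 24.

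Four analyses could use that rule:

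- **Week 16.** Section 3.1: the "final analysis of the efficacy and safety data collected up to week 16 will be performed once all randomised patients have completed" their first 16 weeks. Section 7.4 also limits this lock to data through Week 16.
- **50% interim (optional).** Section 7.4: the "interim database lock and subsequent analysis will be done once the first 50% of the total required number of patients has completed 16 weeks". Its details go to the DMC SAP and charter.
- **75% interim.** Section 7.4: "An additional interim analysis will be performed once the first 75% of patients have completed 16 weeks of the study". Its details go to the TSAP.
- **Week 32.** Section 7.4: "An analysis of the entire trial data will be performed once all randomized patients have completed the 32 weeks of study". Its details also go to the TSAP.

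Two medication provisions bear on Week 24. Section 7.5 counts later data as failure "If a patient takes a rescue medication for the treatment of palmoplantar pustulosis prior to observing the primary endpoint for this trial". Footnote 1 to the restricted-medication table (Section 4.2.2.1) says: "In case of any other acute indication after the Primary Endpoint Visit at Week 16, the use of a restricted medication is permitted".

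**The concern.** Applied mechanically, the rule gives an answer that depends on which visits are in the data set. Take a patient who responds at Week 12, misses Week 16 and responds at Week 24. At the Week 16 lock the success branch cannot operate, and the patient is a failure. In a data set holding Week 24 the patient is a success. At an interim, which branch is open would depend on how early the patient was enrolled.

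The situation can occur: Section 3.3.4.1 foresees patients who stop treatment and come back for only some later visits. Week 24 (Day 169) is also a weak source for a Week 16 value. It is 84 days after the last planned dose (Day 85) and falls after most medication restrictions end. At stake would be a primary endpoint with two values in one clinical trial report, and interim response rates, used for planning later trials, that depend partly on accrual speed.

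**Working it through.** **1. The plan's own figures.** Three independent Binomial(20, p) arms were enumerated exactly. Scenario 1 is met if the better active arm exceeds placebo by at least 4 patients (0.20 × 20). Scenario 2 needs scenario 1 and the 300 mg arm ahead of placebo by at least 3 patients (0.15 × 20). Results for placebo rates 0.15 / 0.20 / 0.25 / 0.30:

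| | Table 7.7:1 | Exact |
|---|---|---|
| Scenario 1, difference 0.30 | 93 / 92 / 91 / 91% | 93.6 / 92.7 / 92.0 / 91.4% |
| Scenario 2, difference 0.30 | 87 / 86 / 85 / 85% | 87.7 / 86.4 / 85.6 / 85.1% |
| Scenario 1, false positive | 11 / 15 / 18 / 20% | 10.8 / 14.5 / 17.2 / 19.1% |
| Scenario 2, false positive | 7 / 10 / 12 / 14% | 6.8 / 9.5 / 11.5 / 13.0% |

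All agree to within about one percentage point. The thresholds belong to 20 patients per arm at the Week 16 analysis.

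**2. What each data set contains.** At the Week 16 lock many patients will already have attended Week 24, but the lock is confined to data through Week 16. Missing is therefore failure for everyone, whatever the enrolment date. For the interims the protocol gives a trigger and no cut-off. For Week 32 it says all data are analysed, not that Week 16 responses are derived again.

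**3. Who could be affected at an interim.** Assume uniform accrual of 60 patients over A weeks. The interim at fraction f falls at week fA + 16, so the number past Week 24 is 60(fA − 8)/A.

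- A = 19.5 weeks (4.5 months): 60(9.75 − 8)/19.5 = 5.4 of 30, and 60(14.625 − 8)/19.5 = 20.4 of 45.
- A = 52 weeks: 60(26 − 8)/52 = 20.8 of 30, and 60(39 − 8)/52 = 35.8 of 45.

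**4. Expected reclassified patients, all arms together.** The protocol gives no missing rate. Assume 5% missing at Week 16 (range 3–10%), with 15–60% of those patients responding at both neighbours.

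| Data set | Low, 5% missing | High, 5% missing | Range, 3–10% missing |
|---|---|---|---|
| 50% interim | 5.4 × 0.05 × 0.15 = 0.04 | 20.8 × 0.05 × 0.60 = 0.62 | 0.02–1.25 |
| 75% interim | 20.4 × 0.05 × 0.15 = 0.15 | 35.8 × 0.05 × 0.60 = 1.07 | 0.09–2.15 |
| Week 32 | 60 × 0.05 × 0.15 = 0.45 | 60 × 0.05 × 0.60 = 1.8 | 0.27–3.6 |

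The interim rows presuppose that Week 24 data are in the lock; the Week 32 row presupposes re-derivation.

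The upper figures are generous. The 60% is the highest single-visit response rate in Table 7.7:1, and success at two visits cannot be more likely than success at either. If response at Weeks 12 and 24 is no commoner than the table assumes for Week 16, the three-arm average is at most (0.60 + 0.60 + 0.30)/3 = 0.50, and the Week 32 figure falls to 60 × 0.05 × 0.50 = 1.5. Permanent dropouts have no Week 24 visit, which lowers it further.

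**5. How much the convention could matter where the threshold is applied.** With 5% missing unrelated to response, counting all missing as failure gives an expected difference of 0.30 × 0.95 = 0.285. The scenario 1 probability is then 92.2% (placebo 0.15) to 89.7% (placebo 0.30). Recovering every missing responder gives 93.6% to 91.4%. The whole gap between the two extremes is 1.4 to 1.7 points, and at the Week 16 lock only the first can occur.

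**The case for a change.** The strongest case for a change is that this is more than an omitted detail. Section 7.5 states the rule, Section 7.4 states the locks, and together they yield values that depend on the data cut. With arms of about 10, 15 and 20 patients, one patient moves a response rate by 0.10 at the 50% interim, 0.07 at the 75% interim and 0.05 at the end. The larger active-minus-placebo difference falls exactly one patient short of 0.20 with probability about 4% if the true difference is 0.30, and about 12% if there is none. One sentence would remove the ambiguity.

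The literal reading stands: nothing in the protocol forbids using Week 24. The rest is weaker.

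- The 0.20 and 0.15 thresholds cannot be held against interim shifts. The 50% interim is judged by a conditional probability and a boundary in the DMC charter. The 75% interim serves planning and has no stated threshold. Neither changes the trial design.
- The one-patient-short probabilities refer to 20 per arm at the Week 16 analysis, where the success branch cannot operate. They would also have to be multiplied by the chance of a reclassification in the arm that matters.
- Sections 4.1.5.2 and 7.4 themselves describe interims at Week 16. That suggests, without proving, that Week 16 data are meant.
- The medication point narrows on inspection. If Week 16 was never observed, rescue for PPP before Week 24 can reasonably be read as taken before the endpoint was observed, so Week 24 is already a failure. What remains is a restricted drug for another acute indication in a patient who was already responding at Week 12. Section 7.5 leaves to the TSAP what counts as a rescue intake that affects efficacy.
- Calling a patient with documented response on both sides a failure is itself a convention, not a correction.

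**Conclusion.** The wording permits two values for the same missing Week 16 response, but no change to the plan is needed. The analysis that carries the primary conclusion is complete as written: at the Week 16 lock a missing response is non-response for every patient, independent of enrolment date and free of anything that happens after Week 16. A second value needs a step the protocol does not prescribe, either recalculating Week 16 for the Week 32 report or letting Week 24 into an interim data set. Derivation rules and data cut-offs are what a TSAP or DMC SAP normally fixes, and Section 7.4 refers these analyses to those documents. The TSAP is planned to be final before the lock for the optional interim.

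On the assumptions above (5% missing, 15–60% responding at both neighbours, uniform accrual over 4.5 to 12 months), fewer than about two patients over all arms would be affected in any data set, and fewer than one at the 50% interim. At 10% missing with the most generous bracket, Week 32 could reach 3.6. The missing rate is not in the protocol, so these sizes are illustrative. That the Week 16 decision is unaffected does not depend on them.

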7.6 RANDOMISATION

Patients will be randomised in blocks to double-blind treatment. Approximately equal numbers of patients will be randomised to each treatment group using a 1:1:1 allocation ratio. BI will arrange for the randomisation and the packaging and labelling of trial medication. The randomisation list will be generated using a validated system, which involves a pseudo-random number generator so that the resulting treatment will be both reproducible and non-predictable. The block size will be documented in the CTR. Access to the codes will be controlled and documented.

Randomisation will be stratified by the presence or absence of plaque psoriasis.

7.7 DETERMINATION OF SAMPLE SIZE

The study is intended to show an increase for BI 655130 over placebo in terms of the proportion of patients achieving a ppPASI50 response at Week 16. There is currently no clinical trial data available in the published literature that describes a placebo response on the ppPASI50 in the population of patients with palmoplantar pustulosis. The success probability for the primary endpoint on this PoCC trial has, therefore, been derived under the assumption that the difference between BI 655130 and Placebo is 0.30 and that a total N of 60 patients (fixed according to feasibility considerations) will be studied in a 1:1:1 ratio (i.e. 20 patients per treatment group).

Simulations in SAS[®] were used to derive estimates of the probability that a single trial would demonstrate an observed difference in proportions between BI 655130 and Placebo that was equal or greater than a defined threshold under a positive scenario whereby the expected difference in proportions is 0.3 in favour of BI 655130. For identifying such a target threshold, a minimum probability of 0.80 was defined. For each trial simulation, the response for each patient on each treatment was generated using a binomial distribution utilizing the expected treatment response rates as noted in [Table 7.7:1](#) below. The trial observed proportions for each treatment were calculated and then the treatment comparisons, according to scenario 1 and scenario 2, were each compared against a range of threshold values using a hierarchical approach. A total of 100,000 trial simulations were performed. In addition, the probability of a false positive declaration being made given the specified target threshold(s), so-called negative scenario, was also determined.

Table 7.7:1 Probability to Achieve the Threshold Difference in Treatments given Expected Treatment Response Rates on ppPASI50 and a Total Sample Size of 60 Patients

Population Response Rate			Expected Response Difference (BI vs PLC)	Threshold (Observed Difference)	Probability Threshold Exceeded ¹	False Positive Rate (%) ²
Low Dose BI	High Dose BI	Placebo				
SCENARIO 1 (maximum of [BI 655130 900 mg or 300 mg] vs. Placebo)						
0.45	0.45	0.15	0.3	0.20	93%	11%
0.50	0.50	0.20	0.3	0.20	92%	15%
0.55	0.55	0.25	0.3	0.20	91%	18%
0.60	0.60	0.30	0.3	0.20	91%	20%
SCENARIO 2 (BI 655130 300 mg vs. Placebo)						
0.45	0.45	0.15	0.3	0.15	87%	7%
0.50	0.50	0.20	0.3	0.15	86%	10%
0.55	0.55	0.25	0.3	0.15	85%	12%
0.60	0.60	0.30	0.3	0.15	85%	14%

Hierarchical testing: scenario 2 only tested if outcome on scenario 1 \geq specified threshold.

¹ Positive scenario: Assuming the expected response rate difference, the probability that the BI 655130 response rate exceeds that of Placebo by at least the threshold amount is displayed.

² Negative scenario: The probability that the BI 655130 response rate exceeds that of Placebo by at least the threshold amount assuming that treatments are equal.

In summary, for a total N of 60 patients, a 1:1:1 allocation ratio to BI 655130 900 mg, BI 655130 300 mg, and Placebo, then under the assumption of a target difference between each dose of BI 655130 and Placebo of 0.30 [positive scenario] for the proportion of responders on the primary endpoint at week 16, this trial will be able to show:

- An observed difference in response rates of at least 0.20, for the maximum of (BI 655130 900 mg and BI 655130 300 mg) versus Placebo, with 91% probability (assuming a Placebo response rate from 0.15 through 0.30). The false positive decision probability in this case ranges from approx. 11%-20% under the assumption of no treatment difference;
- An observed difference in response rates of at least 0.15, for BI 655130 300 mg versus Placebo, with 85% probability (assuming a Placebo response rate from 0.15 through 0.30). The false positive decision probability in this case ranges from approx. 7%-14% under the assumption of no treatment difference.

The hierarchical nature of the comparisons, with rejection of the maximum of (BI 655130 900 mg or BI 655130 300 mg) versus Placebo (scenario 1) required prior to proceeding to the test of BI 655130 300 mg versus Placebo (scenario 2), warrants that the overall success probability is at least 85% while the overall false positive rate [under negative scenario] is controlled at 20% (one-sided).

